^t On trial visit days, the IMP will be administered during the trial visit after trial visit procedures are completed (other than postdose PK/PD sampling); otherwise, the IMP will be self-administered at a set time each day (\pm 2 hours).

^u On trial visit days after Visit 2, IMP compliance for the intervals since the previous visit will be documented using pill counts.

^v Any AEs occurring during the Screening Period will be recorded, and AEs will be solicited/recorded at every trial visit and with any ad hoc telephone contacts

2 Sponsor, Investigators, and Trial Administrative Structure

The administrative structure of the trial is described in the following:

This clinical trial will be sponsored by Merck KGaA, [name]. The trial will be conducted at approximately 50 sites in 10 countries.

Sites to be used will include clinical centers, Phase I units, academic centers, inpatient or outpatient, etc.

The Coordinating Investigator represents all Investigators for decisions and discussions regarding this trial, consistent with the International Council for Harmonisation (ICH) Topic E6 Good Clinical Practice (GCP; hereafter referred to as ICH GCP). The Coordinating Investigator will provide expert medical input and advice relating to trial design and execution and is responsible for the review and signoff of the clinical trial report.

Signature pages for the Protocol Lead and the Coordinating Investigator as well as a list of Sponsor responsible persons are in [Appendix A](#).

The trial will appear in the following clinical trial registries: Clinicaltrials.gov.

PPD will be responsible for the clinical trial documents to be submitted to regulatory authorities, the conduct of the clinical trial, the central laboratory including coordination and distribution of laboratory supplies, drug supply and distribution, data management, statistical analysis, and clinical trial reporting. Further details will be provided in a separate document and updated as necessary. Clinical quality assurance will be performed under the responsibility of the Development Quality Assurance department at Merck KGaA Darmstadt.

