6.2 Dosage and Administration

During the 12-week treatment period, subjects will receive 50 mg bid M2951 or placebo administered as 2 matching oral capsules twice daily for 84 days. Subjects will self-administer the IMP at a set time each day (\pm 2 hours). Subjects must take their daily dose more than 1 hour prior to a meal or snack and more than 2 hours after a meal or snack. Clear fluids are allowed at any time. On trial visit days, the IMP will be administered during the trial visit after the scheduled trial visit procedures (other than post-treatment PK/PD sampling and post-treatment ECGs) are completed.

After completing the treatment period, subjects will be offered the opportunity to participate in an optional 6-month M2951 extension period on Day 85 (Visit 8). Subjects who received M2951 during the treatment period will continue with the same dose of M2951 (in tablet formulation). All subjects in the placebo group during the treatment period will discontinue placebo and start

treatment with 50 mg bid M2951 tablets on Day 85/Day 1 of OLE. On trial visit days, the IMP will be administered during the trial visit after the scheduled trial visit procedures are completed. Subjects will take 2 matching oral tablets twice daily for 6 months. Subjects will self-administer the IMP at a set time each day (\pm 2 hours). Subjects must take their daily dose more than 1 hour prior to a meal or snack and more than 2 hours after a meal or snack. Clear fluids are allowed at any time. On trial visit days, the IMP will be administered during the trial visit after the scheduled trial visit procedures are completed.

If a dose is missed, the subject can take the missed dose up to 6 hours after the scheduled time. If more than 6 hours have elapsed since the dose was missed, the subject should skip the dose for that period, make note of the missed dose, and take the next dose at the regularly scheduled time.

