All other trial-related individuals, ancillary site staff, other clinical research associates/monitors, investigators, Sponsor staff other than those identified above, and PPD staff other than those identified above, will remain blinded to treatment codes or laboratory results capable of revealing treatment. Results from PK and PD testing or the IA will not be reported back to the sites or the PPD study team, with the exception of ESR results. The ESR results will be analyzed at a laboratory local to the site, received by a person at the site independent of study staff at the site, and conveyed to the central laboratory without sharing with study staff at the study site, the Sponsor, or the PPD study team. There will be no communication of results between the PPD study team tasked with conduct of the study and the independent statistician team responsible for the production of IA outputs.

Only when the 12-week Treatment Period is completed for all patients, the data file verified, protocol violations determined, statistical analysis plan (SAP) signed and database partially locked for the 12-week treatment period, will the drug codes be broken and made available, along with laboratory results capable of revealing treatment, for the primary data analysis. The final analysis will be performed after all subjects have completed the Safety Follow-up or discontinued from study early, with assessment of some safety and key efficacy variables.

All breaks of the trial blind must be adequately documented.

Processes to maintain blinding during the IA are described in Section 8.6.

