7.1.2.1 End of Treatment Visit

The End of Treatment Visit (Visit 8) will be performed on Day 85 or within 5 days after early discontinuation of treatment with the IMP. Subjects will undergo the assessments as described in the Schedule of Assessments ([Table 1](#)).

Any ongoing SAEs must be followed up until the SAE/AE has resolved, is considered stable, or is considered no longer clinically relevant by the Investigator.

Subjects opting to participate in the optional extension period will sign a new ICF at this visit. The Investigator will discuss the benefits with the subject and the subject well-being. Subjects are free not to sign the new ICF for the extension period.

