8.6 Interim and Additional Planned Analyses

There will be 3 analyses: (1) an interim analysis (IA), triggered when subjects from the first 50% of the planned enrollment have reached Day 29 of treatment and have available Day 29 hsCRP data, or have discontinued treatment prior to Day 29, (2) a primary analysis, triggered when 100% of subjects enrolled have reached Day 85 of treatment or have discontinued treatment prior to Day 85, and (3) a final analysis, triggered when 100% of subjects enrolled complete all study parts, or discontinue prematurely from study.

Interim Analysis

The percent change in hsCRP from Baseline to Day 29 will be the key endpoint evaluated at the IA. Descriptive statistics will be presented by treatment group. A point estimate and 2-sided 80% CI for the difference Δ in Day 29 hsCRP change from Baseline between subjects treated with M2951+MTX and subjects treated with placebo + MTX will be provided. In addition, the change in DAS28-hsCRP from Baseline to Day 29 will be evaluated using the same approach as used for change in hsCRP. Some safety, baseline characteristics, and disposition data will also be summarized by treatment group at the time of IA.

The results of this IA will be used for internal decision making only and will not impact the conduct of the trial. See Section 6.10 for more details regarding limited unblinding.

Primary Analysis

When the last subject reaches Day 85 of treatment or discontinues from treatment prematurely prior to Day 85, the protocol violations are determined, the SAP is signed, the database is locked for the first 12-week treatment period for all randomized patients for the primary analysis, and the data file verified, the drug codes will be broken and made available for the primary data analysis. All endpoints, demographics and safety data will be analyzed at that time.

Final Analysis

The final analysis will occur only when the last subject completes all study parts, the protocol violations are determined, the database is locked for the final analysis, and the data file verified. Only some safety and key efficacy data will be summarized.

9 Ethical and Regulatory Aspects

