8.3 Primary Analysis

When the last subject has been administered the last dose of IMP during the 12-Week treatment period, the protocol violations are determined, the SAP is signed and the Week 12 database is partially locked for the primary analysis, the drug code will be broken and made available for the primary data analysis. The definition and details of partial database lock for the primary analysis will be documented in the Data Handling Report which will be finalized before the database partial lock for the primary analysis.

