All statistical analyses will be performed by PPD.

Treatment groups and IMP:

Treatment groups are defined as placebo + MTX and M2951 + MTX groups, except for the analyses including both the first 12-week treatment period and OLE period data, which will be summarized according to treatment groups 'Placebo/M2951 + MTX' and 'M2951 + MTX'. Unless otherwise indicated, all analyses will be presented separately for the two treatment groups. The IMPs are placebo and M2951.

Presentation of Tables/Figures

For the primary analysis at the end of first 12-week treatment period, drug code will be broken and tables and figures will be produced using true treatment groups and their true labels (ie, 'Placebo', 'M2951 50 mg BID'). For the final analysis, tables and figures will be produced using true treatment groups and the following labels: 'Placebo/M2951 50 mg BID' and 'M2951 50 mg BID/M2951 50 mg BID'.

Tables and figures will be sorted by treatment group (in order of 'Placebo' and 'M2951 50 mg BID', or 'Placebo/M2951 50 mg BID' and 'M2951 50 mg BID/M2951 50 mg BID' for final analysis) and chronological scheduled time point (where applicable).

Presentation of Listings:

All data recorded during the trial will be presented in individual data listings. All listings are sorted by treatment group (in order of 'Placebo' and 'M2951 50 mg BID', or 'Placebo/M2951 50 mg BID' and 'M2951 50 mg BID/M2951 50 mg BID' for final analysis), subject, and scheduled time point (where applicable), if not otherwise stated.

Data handling for the planned analysis:

For the primary analysis, data will be handled as follows:

- Data from OLE, or safety follow-up posterior to OLE, will be excluded from the primary analysis. This exclusion will be performed at the ADaM level; no selection will be performed, neither at the data management level, nor at the SDTM level.
- As the database lock for the primary analysis will be based on data up to and including the last patient's last dose of IMP (LPLD) during 12-Week treatment period, all data from screening to LPLD during the 12-Week treatment period for all subjects will be locked and available in the database for the primary analysis.
- A cut-off date will be applied at the SDTM level: all data posterior to LPLD during 12-Week treatment period will be removed from the database. Details on the implementation of this cut-off date are available in the document named *SDTM Cut-off date implementation rules_BTKi(M2951)-Compound_v2.0.docx*

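### The SAP cuts primary-analysis data at the last patient's last 12-week dose, while the protocol and the SAP's own synopsis use Day 85; separately, Table 4 closes Month 6 at least one permitted day early

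*SAP*

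**What the plan says.** **Trigger and cut-off.** SAP 8.3 starts the primary analysis "When the last subject has been administered the last dose of IMP during the 12-Week treatment period", once protocol violations are settled, the SAP is signed and the database is partially locked. SAP Section 11 (data handling for the planned analysis) bases that lock on data up to and including this date and adds an SDTM-level cut: "all data posterior to LPLD during 12-Week treatment period will be removed from the database". The mechanics are left to a named cut-off rules document and to a second one: "The definition and details of partial database lock for the primary analysis will be documented in the Data Handling Report".

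Protocol 8.6 starts the same analysis "When the last subject reaches Day 85 of treatment or discontinues from treatment prematurely prior to Day 85". Protocol 6.10 allows the codes to be broken "Only when the 12-week Treatment Period is completed for all patients". The synopsis in SAP Section 6 repeats the Day 85 trigger. SAP Section 9 lists a changed interim-analysis trigger. Its readable text lists no change to the primary-analysis trigger, lock or cut-off, but one item there is blacked out.

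**Dosing and Visit 8.** Protocol 6.2 plans "2 matching oral capsules twice daily for 84 days". Protocol 7.1.2.1 states: "The End of Treatment Visit (Visit 8) will be performed on Day 85". Table 1 footnote t states: "On trial visit days, the IMP will be administered during the trial visit after trial visit procedures are completed". Footnote s says that subjects entering the open-label extension (OLE) receive the OLE tablet at Visit 8.

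**Month 6.** Protocol Table 1 allows ±7 days around Month 6. SAP Table 4 assigns to Month 6 the half-open intervals [135 ; 187) for placebo/M2951 and [219 ; 271) for M2951/M2951. The SAP counts a month as 30 days for time windows.

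**The concern.** The protocol and two sections of the SAP define different data cut-offs for the primary endpoint, and the SAP also disagrees with its own synopsis. If the last double-blind dose is on Day 84 and the visit carrying ACR20 is on Day 85, a cut at the last dose falls before the last completer's endpoint visit. A completer is not set to non-responder under SAP Table 3, so the components would be carried forward from an earlier visit although Day 85 values had been observed. A primary-endpoint cut-off should not hinge on whether one capsule is taken at Visit 8.

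The Month 6 matter is independent of this. A visit made inside the protocol's window can match no analysis visit, and OLE data are not imputed, so the value would drop out of the only time point listed for the OLE efficacy endpoints.

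**Working it through.** **1. Where the last dose and the endpoint visit fall.** Dosing for 84 days from Day 1 ends on Day 84. The endpoint visit is Day 85. The gap is 85 − 84 = 1 day.

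- *Pointing to a loss:* the 84-day duration; the OLE tablet at Visit 8 for OLE entrants; SAP Table 7, which runs the 12-week period only up to the first OLE dose. For an OLE entrant the Visit 8 assessments precede the OLE tablet, so they belong to the 12-week period yet are dated after the last double-blind dose.
- *Pointing to no loss:* visit-day dosing in footnote t; hsCRP sampled predose at Visit 8 (footnote k); ECG predose on Day 85 (Protocol 7.4.4.3); Day 85 described as the final on-treatment visit (Protocol 5.1). With a double-blind dose that day, LPLD is Day 85 and the two triggers coincide.

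If the Day 85 visit is cut, LOCF would normally reach back to Visit 7 (Day 57), the preceding visit with hsCRP.

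**2. How many subjects.** LPLD is read as one calendar date. Assume 60 completers, last-dose dates spread evenly over K weekdays, and Visit 8 on the day after the last dose (assumptions, not from the documents). The cut then reaches everyone sharing the last date:

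E = (60/K) × Σ (j/K)^59 for j = 1 to K ≈ (60/K) / (1 − e^(−60/K))

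| Spread of completion dates | K | Expected number cut |
|---|---|---|
| 60 days | 44 | 1.83 |
| 180 days | 130 | 1.25 |

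Simulation gives the same values, with 1.53, 1.39 and 1.30 at 90, 120 and 150 days.

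**3. Effect on the decision.** Inputs: 30 per arm, 0.46 versus 0.21, rejection if the lower 80% Miettinen-Nurminen limit exceeds zero, with the SAP's factor n/(n−1). Exact enumeration gives power 80.3% (the plan states 80.2%) and type I error 9.3% at 0.21 versus 0.21.

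One responder can matter: 11/30 versus 6/30 has a lower limit of +0.017 (reject), and 10/30 versus 6/30 has −0.014 (do not reject).

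| True rates | Chance that a given subject's status decides the result (active / placebo) | Times a 10–30% chance that Day 57 and Day 85 status differ |
|---|---|---|
| 0.46 vs 0.21 | 0.0761 / 0.0845 | 0.8% to 2.5% |
| 0.21 vs 0.21 | 0.0520 / 0.0526 | 0.5% to 1.6% |

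The 10–30% range is an assumption. These are chances per affected subject, given that the visit is cut. If the chance of a cut were 50% (illustrative), they halve to 0.4–1.3% and 0.3–0.8%.

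**4. Month 6 window.** Rebuilding Table 4 from Days 14, 30, 90 and 180 gives midpoints (14+30)/2 = 22, (30+90)/2 = 60 and (90+180)/2 = 135, and an upper edge of 180 + 7 = 187. Adding 84 gives 106, 144, 219 and 271. All match the printed bounds. Because the intervals are half-open, the last included day is OLE 186 (study 270).

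| Month 6 counted as | Permitted OLE days | Days without a window |
|---|---|---|
| Day 180 (SAP's 30-day month) | 173–187 | 1 of 15 |
| Day 181 | 174–188 | 2 of 15 |
| Day 182 or 183 (26 weeks) | 175–189 or 176–190 | 3 or 4 of 15 |

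In the M2951/M2951 arm, Table 4 counts from the first double-blind dose. As written, each day that OLE Day 1 falls after study Day 85 therefore costs one more: 1 + 5 = 6 of 15 on the 30-day month if OLE starts on Day 90, the last day of the D1-OLE window.

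**The case against.** The best defence on the cut-off is that nothing need be lost. Much of the protocol reads as if a dose is taken on Day 85. SAP Table 11 intends to analyse everything collected up to the start of OLE, and Table 4 accepts Week 12 data through Day 90. The SAP's synopsis keeps Day 85, so the SAP has not simply replaced the trigger. The redacted item in Section 9 could conceivably be a declaration. The two implementation documents are not available here and may retain the visit.

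Most of this stands, and it limits the point to a conflict with a possible loss. It does not remove the conflict. The stated rule is the literal one, and SAP Section 11 makes the later tables depend on data already selected, so Table 11 cannot restore a record removed upstream.

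On Month 6, it is fair that the SAP fixes the month at 30 days for windows. Only the one-day loss follows from its own definition. The larger figures need sites to schedule at 26 weeks (the length Protocol 5.1 gives the extension) or a late OLE start. The readable text does not say that a completer's Visit 8 may be later than Day 85, and the SAP leaves gaps before OLE to case-by-case allocation.

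A wider window also has a cost. For OLE completers, Safety Follow-Up falls from about OLE Day 173 + 28 = 201, safely outside. Subjects who stop OLE early also attend that visit, and their off-treatment values could land in Month 6.

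**Conclusion.** The point holds in this limited form. The trigger, lock and cut-off in SAP 8.3 and 11 contradict Protocol 8.6 and SAP Section 6, and taken literally they can replace an observed Day 85 ACR20 by LOCF. The expected size is zero to about two subjects, under the assumptions on completion dates above. It is nil if a double-blind dose is given at Visit 8 or if the unseen documents keep the visit. Table 4 omits at least one permitted Month 6 day, with no effect on any test because the OLE results are descriptive.

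A reader might infer more than this, and the documents do not support it:

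- *Primary data will be lost.* This depends on Visit 8 dosing and on documents not seen.
- *The trial would be unblinded early.* The trigger alone does not break the code; the SAP must also be signed and the database partially locked.
- *Early discontinuers' ACR20 is affected.* SAP Table 3 already makes them non-responders after discontinuation.
- *Up to six Month 6 days are lost.* Only one follows from the SAP's own month.

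**What to change.** **Cut-off.** Define the trigger and the SDTM cut-off as the last subject's Day 85/End of Treatment visit. Use the same wording in SAP Sections 6, 8.3 and 11 and in the cut-off rules document, and state that all predose Visit 8 assessments are kept. Align the Data Handling Report. If a last-dose trigger is really intended, declare it in SAP Section 9. The passages on dosing at Visit 8 should be reconciled, but the cut-off should work whichever way that is settled.

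**Month 6.** Extend the upper bounds to at least [135 ; 188) and [219 ; 272). If Month 6 is scheduled at 26 weeks, extend them through OLE Day 190, that is [135 ; 191) and [219 ; 275), since 190 + 84 = 274. Assign only Visit 12 data, not Safety Follow-Up data, to Month 6. Counting the M2951/M2951 windows from OLE Day 1 would also absorb a late start, but that is partly a matter of preference.

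**Cost.** A few lines in the SAP and the cut-off specification, no new data, and at most a few days' delay to the cut-off.

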- For all subjects, data during the 12-week treatment period up to and including the LPLD will be included for the primary analysis except for the safety follow-up data. All safety follow-up data will be reported for the mITT population at the final analysis stage.
- Data selection for the primary and final analyses will be identified at the ADaM level first before any statistical calculations can start. Therefore, the data handlings described in all tables in the following sections of this SAP will depend on data selected in the ADaM level.

For the final analysis, data will be presented on subjects who agreed to participate in OLE.

Presentation of continuous and qualitative variables:

Continuous variables will be summarized using descriptive statistics, ie

- number of subjects (N)
- number and percentage of non-missing values
- number and percentage of missing values
- mean, standard deviation (SD)
- median, 25th Percentile - 75th Percentile (Q1-Q3)
- minimum and maximum

For both continuous and qualitative variables, percentages such as 0% or 100% should be reported with the same format used for the column, together with the count of observations. For example, if the count of observations is zero, then display '0 (0.0)'; if the count of observations represents 100%, then display 'xx (100.0)'.

Qualitative variables will be summarized by counts and percentages. Unless otherwise stated, the calculation of proportions will be based on the number of subjects in the analysis set of interest. Therefore counts of missing observations will be included in the denominator and presented as a separate category.

In case the analysis refers only to certain visits, percentages will be based on the number of subjects in the analysis set of interest, unless otherwise specified. Total of missing and non-missing observations at each time-point will reflect the population still in the trial at that time. For example, if a subject is still in the trial at the time-point but with missing data, it should be counted in the number of missing observations.

Pharmacodynamic endpoints will be reported as described above for presentation of continuous and qualitative variables.

Specific rules for PK concentrations and PK parameters

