In all subject data listings, imputed values will be presented. In all listings imputed information will be flagged. Non imputed partial dates will be presented in a format such as “____YYYY”. Where imputation is defined, an imputed date with flag (ie, D for day, M for month) will be reported.

Missing statistics, eg when they cannot be calculated, should be presented as ‘nd’ (denoting “not done”). For example, if n=1, the measure of variability (SD) cannot be computed and should be presented as ‘nd’.

In case of zero records, an empty output with 0 occurrences, or a sentence mentioning that there are no data, will be presented. For tables of AEs and Deaths (outputs required for EudraCT and/or clinicaltrial.gov), if there are no observations, the output must contain the first line ‘Subject with...’ or ‘Subject who died’ displayed with 0 occurrence.

If the System Organ Class (SOC) or Anatomical Therapeutic Class (ATC) term is missing/not coded yet, then 'Uncoded SOC' (or 'Uncoded ATC') will be indicated at the ADaM level. When a Preferred Term (PT) is missing, it will be set to 'Uncoded PT: verbatim text'.

Treatment day:

Treatment day is defined as relative day to the start date of treatment. Treatment day will be calculated accordingly, ie:

- For primary analysis, treatment day 1 is defined as the date of first administration of any IMP.
- For final analysis, treatment day 1 is defined as the first administration of M2951:
 - For subjects who switch from placebo to M2951, the treatment day 1 will be defined as the first administration of M2951 in OLE period
 - For subjects who have taken M2951 during 12-Week treatment period and continue with the same treatment during OLE, the treatment day 1 will be defined as the first administration of M2951 during 12-Week treatment period

The day before is defined as Treatment day -1 (no Treatment day 0 is defined).

Repeated and unscheduled measurements:

Data collected at unscheduled visits will be included and analyzed for safety analyses in the same fashion as the data collected at scheduled visits. Unscheduled measurements will also be used for shift tables.

Gap between 12-Week treatment period and OLE period

Subjects with a gap strictly greater than 4 weeks between 12-Week treatment period and OLE period will be analyzed the same way as subjects without a gap. Specific data listings on safety data (AEs and all laboratory data) will be produced for these subjects for the final analysis.

Time windows

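### Safety follow-up data of subjects who do not enter the open-label extension have no clear place in any by-arm safety table

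*SAP*

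**What the plan says.** **Protocol.** The Synopsis and Section 4.3.1 count safety from consent to the Safety Follow-Up Visit. Sections 8.4 and 8.5.5 use the Safety Analysis Set for the primary analysis and the OLE Safety Analysis Set for the final one.

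**SAP, primary analysis.** Section 11 (data handling) states that 12-week data "will be included for the primary analysis except for the safety follow-up data". Its first bullet is narrower: "Data from OLE, or safety follow-up posterior to OLE, will be excluded from the primary analysis". A cut-off is set at the last patient's last dose (LPLD): "all data posterior to LPLD during 12-Week treatment period will be removed from the database". Table 15 ends the primary safety period at OLE start or at discontinuation of treatment. Table 16 runs the TEAE window to the end of study for subjects who decline the OLE, then in the same cell restricts it to events of the 12-week period.

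**SAP, final analysis.** Section 11 says "All safety follow-up data will be reported for the mITT population at the final analysis stage", and shortly afterwards "For the final analysis, data will be presented on subjects who agreed to participate in OLE". Section 10.2 and Table 15 place final safety on the OLE safety set. Table 1 assigns safety analyses to the SAF and OLE SAF only. The final-analysis column labels are Placebo/M2951 and M2951/M2951.

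**The concern.** Non-entrants, meaning subjects who complete 12 weeks and decline the OLE or who stop treatment early, still attend the Safety Follow-Up Visit. Adverse events, hematology, chemistry and vital signs are collected there. The protocol counts that period in its safety endpoints, but the SAP removes it from the primary tables and then gives it no workable home in the final ones.

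These subjects are not a random subset. Protocol Section 6.5.4 lists laboratory findings that lead to withdrawal of IMP, so early discontinuers may include the subjects whose follow-up values show whether an abnormality resolved. Two programmers who start from different sentences of the SAP could also produce different TEAE counts for the same arm.

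**Working it through.** **Tracing a non-entrant's follow-up data through the rules**

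| Stage | Rule that would include the data | Rules against |
|---|---|---|
| Primary | Table 16, first sentence (decliners' AEs to end of study); first bullet of Section 11 data handling, which excludes only the OLE and follow-up after it | Section 11 sentence excluding follow-up for all subjects; Table 15 period; Table 16 restriction to 12-week events; LPLD cut-off |
| Final | Section 11 sentence sending follow-up to mITT | Section 11 limit to OLE participants; Section 10.2 and Table 15 (OLE SAF); Table 1 (no safety analysis on mITT); no column for non-entrants |

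Every route in is contradicted by another rule. The Table 16 route is also narrow: it names decliners but not early discontinuers, and it covers adverse events but not laboratory or vital-sign values. The mITT set is an efficacy set, analysed as randomized, and it requires a postdose ACR20 evaluation. The SAP analyses safety as treated.

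**Share of time affected** (84 days of treatment and 28 of follow-up, Protocol Section 5.1)

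- Completer who declines the OLE: 28 / (84 + 28) = 28/112 = 25%.
- Illustration, last dose on Day 28: 28 / (28 + 28) = 28/56 = 50%.

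**What the cut-off removes even if Table 16 prevails.** Let L be LPLD and let a subject's last dose fall k days earlier. Follow-up runs from day L − k + 1 to L − k + 28, so the days after L number 28 − k (none once k reaches 28).

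| k (days before LPLD) | Follow-up days removed |
|---|---|
| 0 | 28 |
| 7 | 21 |
| 14 | 14 |
| 28 or more | 0 |

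**Number of subjects.** OLE uptake is not stated. If it is assumed to lie between 90% and 50% of the 64 planned subjects, non-entrants number 64 × 0.10 = 6.4 to 64 × 0.50 = 32, or 25.6 to 128 person-weeks at 4 weeks each.

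**Visit windows.** Table 4 counts from first dose and has no follow-up visit. A follow-up value near Day 56 from the Day 28 stopper falls in [49; 70), labelled Week 8, as though on treatment. A completer's value near Day 112 falls in no primary-analysis window.

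**The case against.** The strongest reply is that the sentence sending all follow-up data to the final analysis is a specific exception to the general limit to OLE participants. Tables 5 and 6 lend support: decliners' completion of follow-up is counted at both stages, and SAF and mITT counts appear at the final analysis. On that reading the defect is a wrongly named set and missing table specifications. But those tables give only disposition and set counts. No safety table, Table 1 entry or column label implements the exception.

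Second, Protocol Section 8.3.2 lists the safety endpoints under the double-blind treatment period without a follow-up end point. The Synopsis, however, uses the same heading and states the window to the Safety Follow-Up Visit.

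Third, the restriction to the OLE safety set comes from Protocol Sections 8.4 and 8.5.5, and Section 8.6 promises only some safety data at the final analysis. This stands: the fix departs from the protocol and must be recorded as such.

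Fourth, nothing is lost outright. The SAP states that "All data recorded during the trial will be presented in individual data listings", Section 17.1 lets later information such as a fatal outcome be presented separately, and Section 17.2.1 summarizes all deaths. This also stands, and it limits the point to by-arm summaries.

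Fifth, the day shares are illustrations, and the cut-off affects only non-entrants dosed within 28 days of LPLD. Both statements are correct. The lock report and cut-off rules were not supplied and may hold further detail, but the contradictory sentences are in the SAP itself.

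**Conclusion.** The concern holds and should be fixed. Read together, the SAP's rules leave non-entrants' follow-up adverse events, serious events, laboratory values and vital signs without an uncontradicted by-arm table, although the protocol's safety endpoints reach that visit. The affected window is 25% of the post-first-dose period for a completer who declines the OLE, and proportionately more for early stoppers. How many subjects this touches depends on OLE uptake and early discontinuation, which are not given. The number of dosed subjects lost by using mITT is also unknown. It is probably small, because early stoppers return for an End of Treatment Visit. Efficacy conclusions do not depend on this point.

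**What to change.** At the final analysis, add a double-blind safety summary (AEs, SAEs, laboratory, vital signs) on the full SAF, as treated, from first dose to the Safety Follow-Up Visit or first OLE dose. Show post-treatment events separately, because only non-entrants and OLE entrants with a treatment gap have off-treatment time. Rewording the primary-analysis rules alone would not do, since follow-up after LPLD cannot enter those tables.

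1. Section 11, data handling: replace mITT by SAF in the follow-up sentence, and exempt this summary from the limit to OLE participants.
2. Section 10.2 and Table 15: add the SAF at the final analysis for this summary.
3. Table 16: give one TEAE end rule that covers decliners and early discontinuers.
4. Table 4: add a follow-up visit counted from last dose. Use the primary-analysis rows for the 12-week visits, since the final-analysis row for Placebo/M2951 reads NA.
5. Section 11, presentation: use the Placebo and M2951 50 mg BID columns for this summary.
6. Section 11, treatment day: the SAP says "For final analysis, treatment day 1 is defined as the first administration of M2951", which is undefined for placebo non-entrants. Use first dose of any IMP here.
7. Section 9: record the departure from Protocol Sections 8.4 and 8.5.5.

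If exposure-adjusted rates (Section 17.1.1) are shown for this summary, state which person-time goes with the on-treatment and post-treatment windows.

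The cost is SAP wording in eight places (plus that sentence if needed), a follow-up visit derivation, post-treatment displays and one SAF table set with its own columns. No new data or visits are needed.
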